5.0 THERAPEUTIC/DIAGNOSTIC AGENTS & NON-THERAPEUTIC ASSESSMENTS

5.1 Mirdametinib

This study utilizes the investigational agent PD-0325901 (mirdametinib) to be supplied by SpringWorks. The IND # for PD-0325901 (mirdametinib) is 139883 (Neurofibromatosis Type 1).

On January 19, 2018, SpringWorks Subsidiary 3, PBC (SpringWorks) accepted an IND transfer and agreed to assume all sponsor and regulatory responsibilities for IND 066809 (Cancer) and drug product, PD-0325901, previously held by Pfizer.

Only subjects enrolled in the study, who meet study entry criteria (Sections 6.1 and 6.2) may receive study treatment. Only authorized Site personnel may supply or administer study treatment.

Treatment Name	Mirdametinib (PD-0325901)
Type	Drug
Dose Formulation	Capsule
Unit Dose Strength(s)	1 mg and 2 mg
Dosage Level(s)	See the planned doses for each Dose Level escalation (Section 4.2)
Route of Administration	Oral
Frequency of Administration	Twice daily (BID)

Memorial Sloan Kettering Cancer Center
[name]
[name]

Sourcing	SpringWorks will provide MSK with mirdametinib for individual subject distribution.
Packaging and Labeling	Mirdametinib will be provided in 75 count bottles. Each bottle will be labeled as required per country requirement.
Former Names	PD-0325901-00, PD-0325901-0000, PF-00192513-00

Preparation:

- Mirdametinib does not require special preparation by pharmacy personnel prior to dispensing to subjects.
- Mirdametinib will be supplied as hard gelatin capsules (1- and 2-mg) for oral administration.
- Mirdametinib will be packaged in high-density polyethylene bottles.
- Subjects will be instructed to keep their mirdametinib in the original bottles and not transfer it to any secondary containers.

Handling:

- No special handling of mirdametinib is required.

Storage:

- Mirdametinib must be stored at 15°C to 25°C (59°F to 77°F).
- The Investigator must confirm appropriate temperature conditions have been maintained during transit for all mirdametinib received and any discrepancies are reported and resolved before use of the study treatment.
- All mirdametinib must be stored in a secure, environmentally controlled, and monitored (manual or automated) area in accordance with the labeled storage conditions with access limited to the investigator and authorized site staff.

Accountability:

- The Investigator or designee is responsible for mirdametinib accountability, reconciliation, and record maintenance (i.e., receipt, reconciliation, and final disposition records).
- Subjects will be instructed not to dispose of any mirdametinib treatment bottles, and to bring all bottles (used and unused) back to the site at every visit.
- Accountability will be performed by site personnel at each dispensing visit as described in the SoA (Section 11). If issues with the subject's compliance with mirdametinib are detected, subjects will be re-educated about the importance of following the prescribed dosing regimen.
- Returned mirdametinib will not be re-dispensed to the subjects.

Memorial Sloan Kettering Cancer Center
[name]
[name]

5.2 Fulvestrant (Faslodex)

Fulvestrant will be administered in Arm 1 by intramuscular (IM) injection at the dose and regimen approved by the FDA for the treatment of ER-positive metastatic breast cancer (500mg on Day 1 and Day 15 of Cycle 1 and on Day 1 of all subsequent cycles).

Fulvestrant is supplied as two 5 mL clear neutral glass (Type 1) barrels, each containing 250 mg/5 mL of Fulvestrant solution for intramuscular injection and fitted with a tamper evident closure. The single-dose prefilled syringes are presented in a tray with polystyrene plunger rod and safety needles (SafetyGlide™) for connection to the barrel. Discard each syringe after use. If a patient dose requires only one syringe, unused syringe should be stored as directed below.

Storage: REFRIGERATE, 2°-8°C (36°-46°F). TO PROTECT FROM LIGHT, STORE IN THE ORIGINAL CARTON UNTIL TIME OF USE.

Refer to the package insert for additional details regarding Fulvestrant administration.

5.3 FDA Application

This study utilizes the investigational agent PD-0325901 (mirdametinib) to be supplied by SpringWorks. The IND # for PD-0325901 (mirdametinib) is 139883 (Neurofibromatosis Type 1) and 066809 (Cancer). Memorial Sloan Kettering Cancer Center will submit a Cross Reference Application to the FDA for the investigational use of PD-0325901 (mirdametinib) as monotherapy and in combination with fulvestrant.

6.0 CRITERIA FOR PARTICIPANT ELIGIBILITY

Eligible patients must meet all of the inclusion criteria and cannot meet any of the exclusion criteria before the start of treatment.

Where applicable, the CTCAE V.5.0 classification should be used to interpret the severity grades used as limits for eligibility.

6.1 Participant Inclusion Criteria

Subjects are eligible to start the treatment in the study only if all of the following criteria apply:

Arm 1 (metastatic breast cancer):

- Female adults (≥ 18 years of age on the date of informed consent)
- Postmenopausal or receiving ovarian suppression (including GnRH agonists such as goserelin)
- Histologically confirmed hormone receptor-positive metastatic breast cancer with evidence of progression on at least 1 prior line of therapy for metastatic disease which should have included a CDK4/6 inhibitor in combination with endocrine therapy. Prior chemotherapy is permitted.
- ER+ as defined by immunohistochemistry (IHC) $\geq 1\%$ by local laboratory testing (as per the ASCO-CAP guidelines)

Memorial Sloan Kettering Cancer Center
[name]
[name]

- HER2-negative, as defined by the negative in situ hybridization test (FISH, CISH, or SISH) or an IHC status of 0, 1+ or 2+ by local laboratory testing. If IHC is 2+ (i.e. indeterminate), then a negative in situ hybridization test (FISH, CISH, or SISH) is required (as per the ASCO-CAP guidelines).
- NF1 loss of function or another MAPK-activating genomic alteration documented by a CLIA-certified NGS assay at any time before the start of treatment. Note: archival tissue, if available and collected within 6 months of enrollment, may be used for this testing in lieu of fresh tissue.

Arm 2 (advanced solid cancers):

- Male or female adults (≥ 18 years of age on the date of informed consent)
- Histologically confirmed advanced, metastatic solid tumor cancer for which there is no available therapy known to confer clinical benefit. Colorectal, anal, small bowel, biliary or ampullary cancers are not eligible.
- Class 1 or class 2 MEK1 or MEK2 mutations, as described below, documented by a CLIA-certified NGS assay at any time before the start of treatment. Class 3 MEK1 or MEK2 mutations as described in that paper are excluded. A complete list of the mutations allowed based on that paper can be found below, however, rare mutations not listed in this table may be permitted at the discretion of the principal investigator of the study. Note: archival tissue, if available and collected within 6 months of enrollment, may be used for this testing in lieu of fresh tissue.

Class 1 – Permitted	Class 2 – Permitted	Class 3 - Excluded
MEK1 D67N	MEK1 K57N	MEK1 Δ L98-I103
MEK1 P124L	MEK1 C121S	MEK1 Δ I99-K104
MEK1 P124S	MEK1 F53L	MEK1 Δ E102-I103
	MEK1 Q56P	

The permitted mutations shown above are for MEK1. MEK1 and MEK2 are closely related, are structurally similar, share 79% amino acid identity, and they share equal ability to phosphorylate their ERK substrates³⁰. While the experiments performed above classify individual MEK1 mutations only, the class 3 mutations in MEK1 all share in-frame deletions that remove a potent negative regulatory element of MEK1. These are easily distinguishable from other mutations in MEK1. Therefore, the identification of exclusionary class 3 MEK2 alterations will be straightforward as well, with paralogous mutant residues in MEK1 and MEK2 defined in the manuscript above. A table showing the permitted enrolling paralogous class 1 and class 2 residues are shown in the table below, again with the caveat that rare mutations in MEK2 not listed in the table below may be eligible at the discretion of the principal investigator.

MEK1	MEK2
F53	F57
Q56	Q60
K57	K61

Memorial Sloan Kettering Cancer Center
[name]
[name]

V60	V64
D67	D71
C121	C125
P124	P128
Y130	Y134
E203	E207

All Arms:

- Patient (or Legally Authorized Representative [LAR]) must sign written informed consent form before any study-specific procedure is performed
- ECOG performance score of 0 or 1
- Life expectancy of ≥ 3 months
- At least one tumor lesion measurable by RECIST 1.1. A lesion in a previously irradiated area may be considered as measurable disease if there is objective evidence of progression of the lesion by RECIST 1.1 (*Eisenhauer EA et al, 2009*) between the prior radiotherapy and the screening CT or MRI scan.
- Adequate bone marrow function at screening, as determined by:
 - Absolute neutrophil count (ANC) $>1,500/\text{mm}^3$ (CTCAE Grade ≤ 1)
 - Platelet count $>100,000 \text{ mm}^3$
 - Hemoglobin $>9.0 \text{ mg/dL}$
- Adequate kidney function at screening, as determined by
 - Estimated glomerular filtration rate (eGFR) $>60 \text{ mL/min}/1.73 \text{ m}^2$ calculated by the CKD-EPI equation (CTCAE Grade ≤ 1).
- Adequate hepatic function at screening, as determined by:
 - Total bilirubin $\leq 1.5 \times \text{ULN}$ if baseline was normal or $\leq 1.5 \times \text{baseline}$ if baseline was abnormal (CTCAE Grade ≤ 1). Patients with previously documented Gilbert's Syndrome may have total bilirubin $\leq 3 \times \text{ULN}$.
 - AST $\leq 3.0 \times \text{ULN}$ if baseline was normal or $\leq 3.0 \times \text{baseline}$ if baseline was abnormal (CTCAE Grade ≤ 1).
 - ALT $\leq 3.0 \times \text{ULN}$ if baseline was normal or $\leq 3.0 \times \text{baseline}$ if baseline was abnormal (CTCAE Grade ≤ 1).
- Adequate coagulation function at screening, as determined by:
 - INR $\leq 1.5 \times \text{ULN}$ if not on anticoagulant therapy or $>1.5 \times \text{baseline}$ if on anticoagulant therapy (CTCAE Grade ≤ 1). If the patient receives anticoagulant therapy, the dose must be stable for at least 2 weeks before the start of treatment.
 - PTT $\leq 1.5 \times \text{ULN}$
- Adequate cardiac function at screening, as determined by:
 - Systolic blood pressure $<150 \text{ mmHg}$ and diastolic blood pressure $<90 \text{ mmHg}$ (CTCAE Grade ≤ 1).

Note: Anti-hypertensive medications are permitted, and if a patient does not meet these eligibility criteria at time of screening, treatment with additional anti-hypertensive agents is permissible at the discretion of the investigator,

and blood pressure can be rechecked at a subsequent visit. Measured blood pressures that fall out of this range after screening do not render patients ineligible, however every effort should be made to medically manage these elevated blood pressures at the investigator's discretion.

- LVEF $\geq 50\%$ by MUGA or ECHO.
- No clinically significant ECG waveform abnormalities at the investigator's discretion
- QTcF ≤ 470 ms
- Adequate serum lipid profile at screening, as determined by
 - Serum cholesterol < 300 mg/dL
 - Serum triglycerides < 300 mg/dL
- Adequate glycemic control at screening, as determined by
 - Fasting blood glucose < 140 mg/dL **or**
 - Random blood glucose < 250 mg/dL

Note: Anti-hyperglycemic medications are permitted if a patient does not meet these eligibility criteria at time of screening. Blood glucose measurements that fall out of this range do not render patients ineligible, and appropriate glycemic control at subsequent visits is at the discretion of the investigator.
- Blood calcium and phosphate levels within normal levels per institutional lab standard at screening (calcium level may be corrected for albumin at the investigator's discretion)
- Adequate ophthalmological exam in both eyes at screening, as determined by
 - Intraocular pressure ≤ 21 mmHg
 - No clinically significant abnormalities on the ocular tomography (OCT), including no evidence of ocular abnormality that would be considered a significant risk factor for central serous retinopathy, retinal vein occlusion (RVO), or neovascular macular degeneration (mild and controlled / stable age-related macular degeneration may be acceptable at the investigator's discretion).
- Able and willing to comply with all aspects of the protocol

Contraception and Pregnancy Testing

Arm 1 (ER-positive metastatic breast cancer):

- Not applicable (subjects must be female and postmenopausal or receiving ovarian suppression)

Arm 2 (advanced solid cancers with MEK1 or MEK2 mutations):

- Male subjects must agree to the following during the treatment period and **for at least 6 months** after the last dose of study treatment:
 - Refrain from donating sperm

AND either:

Memorial Sloan Kettering Cancer Center
[name]
[name]

- Be abstinent from heterosexual intercourse as their preferred and usual lifestyle (abstinent on a long term and persistent basis) and agree to remain abstinent
OR
- Must agree to use a male condom when having sexual intercourse with a woman of childbearing potential (WOCBP).
- Women of childbearing potential (WOCBP) must
 - Have a negative pregnancy test at screening and within 72 hours before the start of treatment
AND
 - Must agree to use a contraceptive method that is highly effective during the treatment period and for at least 6 months after the last dose of study treatment. Suitable methods of contraception are described in Section 11.5
AND
 - Must agree not to donate eggs (ova, oocytes) for the purpose of reproduction during the study and for a period of 6 months after last dose of study treatment.

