7.1 Research Participant Registration

Confirm eligibility as defined in the section entitled Inclusion/Exclusion Criteria. Obtain informed consent, by following procedures defined in section entitled Informed Consent Procedures. During the registration process registering individuals will be required to complete a protocol specific Eligibility Checklist. The individual signing the Eligibility Checklist is confirming whether the participant is eligible to enroll in the study. Study staff are responsible for ensuring that all institutional requirements necessary to enroll a participant to the study have been completed. See related Clinical Research Policy and Procedure #401 (Protocol Participant Registration).

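### The INR inclusion limit for anticoagulated patients is written as a floor (>1.5 × baseline) and, apart from its Grade ≤1 bracket, sets no upper limit

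*Combined protocol and SAP*

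**What the plan says.** The coagulation item in Section 6.1 opens with "Adequate coagulation function at screening, as determined by". Its INR line has two branches. Off anticoagulants, INR may be at most 1.5 × ULN. The line continues "if not on anticoagulant therapy or $>1.5 \times \text{baseline}$ if on anticoagulant therapy (CTCAE Grade", and the bracket ends in ≤1. The next sentence reads "If the patient receives anticoagulant therapy, the dose must be stable for at least 2 weeks before the start of treatment". The PTT limit that follows is a ceiling of 1.5 × ULN.

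The neighbouring hepatic limits have the same two-branch form, with a ceiling in both branches. For bilirubin the text after the ULN limit is "if baseline was normal or $\leq 1.5 \times \text{baseline}$ if baseline was abnormal". The transaminase limits follow suit: "ALT $\leq 3.0 \times \text{ULN}$ if baseline was normal or $\leq 3.0 \times \text{baseline}$ if baseline was abnormal".

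The criteria are binding. Section 6.1 begins "Subjects are eligible to start the treatment in the study only if all of the following criteria apply", and Section 7.1 says "The individual signing the Eligibility Checklist is confirming whether the participant is eligible to enroll in the study". On the grade brackets, Section 6.0 says "Where applicable, the CTCAE V.5.0 classification should be used to interpret the severity grades used as limits for eligibility".

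**The concern.** A high INR is the unsafe direction for bleeding, so a limit meant to secure adequate coagulation should be a maximum. For anticoagulated patients the printed limit is a minimum.

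Two things are at stake. First, the stable-dose sentence shows that patients on steady anticoagulation are meant to be admissible. If baseline is the INR on that steady dose, such a patient sits near 1.0 × baseline and fails. Staff must then either exclude a patient the protocol intends to admit or enrol against the printed criterion. Second, apart from the grade bracket, the line places no upper limit on INR in a group where bleeding risk matters. Section 15.5 itself advises caution with intramuscular fulvestrant in anticoagulant users (Arm 1), and Section 9.0 calls for a pre-treatment biopsy, where safe, if suitable archival tissue is lacking.

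**Working it through.** The plan states no figure to reproduce. The check covers the direction of the inequalities and the consequence of the printed one.

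**1. Direction of comparable limits.** All limits in Section 6.1 written as multiples of ULN or baseline:

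| Test | Multiple of ULN | Multiple of baseline |
|---|---|---|
| Total bilirubin | ≤1.5; ≤3 (Gilbert's) | ≤1.5 |
| AST | ≤3.0 | ≤3.0 |
| ALT | ≤3.0 | ≤3.0 |
| INR | ≤1.5 (off anticoagulant) | **>1.5** (on anticoagulant) |
| PTT | ≤1.5 | none |

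The total is 3 + 2 + 2 + 2 + 1 = 10, with nine ceilings and one floor. Among the four baseline multiples, three are ceilings and one is a floor. The minimum values for neutrophils, platelets, haemoglobin, eGFR and LVEF are not parallels, because low values are the unsafe direction there.

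**2. Printed rule against intended rule.** Let r = screening INR ÷ baseline INR for a patient on an anticoagulant. Before the bracket is applied:

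| r | Printed: pass if r > 1.5 | Intended: pass if r ≤ 1.5 |
|---|---|---|
| 1.0, 1.25, 1.5 | fail | pass |
| 1.51, 2, 3, 5 | pass | fail |

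The rules are exact complements, so they disagree at every r, whatever baseline means. The meaning of baseline decides only which patients fall on each side. If it is the INR on the stable dose, a stable patient has r near 1.0 and fails. If it is the INR before anticoagulation, some stable patients could exceed 1.5 and pass.

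**3. Effect of the Grade ≤1 bracket.** The document does not print the CTCAE cut-offs for INR. Assume the upper end of Grade 1 is some multiple g of baseline.

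- If g ≤ 1.5, the floor and the bracket contradict each other and no anticoagulated patient qualifies.
- If g > 1.5, only patients with 1.5 < r ≤ g qualify.

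In both cases every patient with r ≤ 1.5 is still rejected.

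The nearest printed analogue suggests the first case. For bilirubin, Table 4 in Section 15.4 labels values above 1.5 and up to 3.0 × baseline as Grade 2, while Section 6.1 pairs ≤1.5 × baseline with Grade ≤1. This is an analogy from another analyte and does not establish the INR grades.

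**4. Search for a correction.** No other part of the document states an INR limit. Section 6.0 explains how to read grades but does not reverse an inequality. The PTT ceiling is a separate test.

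**The case against.** The strongest reply is that the practical exposure is small. The Grade ≤1 bracket is itself an upper limit in the same sentence. Section 6.2 also excludes current toxicity above Grade 1, and any laboratory abnormality that the investigator thinks raises the risk of participation. The heading, the stable-dose sentence and the neighbouring ceilings all point to the intended direction, and experienced staff will probably read the line as ≤. The complete disagreement between the two rules holds only before the bracket is applied, and the real disagreement cannot be calculated without the INR grades.

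Much of this stands. It limits the safety consequence, and nothing here shows that over-anticoagulated patients would be treated. It does not cure the line, because the bracket and the exclusions can only remove patients. None of them admits the stable patient whom the floor rejects.

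Two further points can be raised. Baseline is also undefined for bilirubin, AST and ALT, and a footnote to the schedule of assessments ties baseline characteristics to Cycle 1 Day 1. That footnote concerns descriptive characteristics and cannot serve a criterion judged at screening. Nor is the corrected ceiling strict: with assumed baseline INRs of 2.0, 2.5 and 3.0, multiplying by 1.5 gives 3.0, 3.75 and 4.5. That bears on how much protection the multiple gives, and does not support keeping it as a floor.

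A misread sign in the text extraction cannot be fully excluded. The ≤ signs in the same line and in the lines on either side were read correctly, and a look at the source page settles it.

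**Conclusion.** The concern holds. The INR limit for anticoagulated patients is wrong as printed. It is the only floor among ten ULN or baseline multiples, and the only one of four baseline multiples that points that way. Before the bracket it reverses the classification of every anticoagulated patient, and after the bracket it still rejects everyone at or below 1.5 × baseline. That a stable patient fails rests on reading baseline as the INR on the stable dose. That the bracket conflicts with the floor rests on the bilirubin analogy alone.

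The number of patients affected cannot be stated, because the document does not say how many will be anticoagulated. The consequence is confined to eligibility and its documentation. It should be corrected because the threshold is operative, though it is probably a slip.

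**What to change.** In Section 6.1, amend the INR line to: *INR ≤1.5 × ULN if not on anticoagulant therapy, or ≤1.5 × baseline if on anticoagulant therapy (CTCAE Grade ≤1)*. Add that baseline here is the patient's established INR on the stable anticoagulant dose. That definition is a recommendation that fits the stable-dose sentence; the document does not supply one. Then confirm that the eligibility checklist carries the same wording.

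The cost is one symbol, one defining phrase and a checklist check. The design and the analysis are unchanged.

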11.5 Pregnancy Testing

For females of childbearing potential, negative serum pregnancy test is required at screening and within 72 hours of starting treatment. Serum pregnancy testing will be performed on Day 1 of each cycle and at EOT for females of childbearing potential. If the clinic standard is to do a serum pregnancy test more frequently, that is acceptable with the protocol as written.

Male and female patients should start using birth control from screening throughout the study period up to 6 months after the last dose of study drug. If there is any question that a patient will not reliably comply with the contraception requirements, they should not be enrolled in the study, and any patient who becomes pregnant should be withdrawn from the study. Any pregnancies that occur within 6 months post-treatment discontinuation are to be reported.

Patients of childbearing potential, who are sexually active, and their partners must agree to the use of a highly effective form of contraception throughout their participation during the study treatment and for 6 months after the last dose of study drug(s):

- Combined (estrogen- and progestogen-containing) hormonal contraception associated with inhibition of ovulation:

Memorial Sloan Kettering Cancer Center
[name]
[name]

- Progestogen-only hormonal contraception associated with inhibition of ovulation
- Intrauterine device (either copper or hormone-based)
- Bilateral tubal occlusion
- Vasectomized partner
- Sexual abstinence if it is the preferred and usual lifestyle of the patient

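### Section 6.1 waives contraception and pregnancy testing for all of Arm 1, including women who qualify only through ovarian suppression, and childbearing potential is never defined

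*Combined protocol and SAP*

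**What the plan says.** **Who may enter Arm 1.** Section 6.1 requires the patient to be "Postmenopausal or receiving ovarian suppression (including GnRH agonists such as goserelin)". The second branch admits women who have not reached menopause. It does not say that suppression must continue.

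**What 6.1 asks of them.** Under its contraception and pregnancy testing heading, the whole Arm 1 entry is "Not applicable (subjects must be female and postmenopausal or receiving ovarian suppression)". For Arm 2, which receives the same investigational drug, women of childbearing potential need two negative pre-treatment tests, highly effective contraception until 6 months after the last dose, and an undertaking not to donate eggs.

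**What 11.5 asks.** It names no arm.
- Testing before treatment: "For females of childbearing potential, negative serum pregnancy test is required at screening and within 72 hours of starting treatment".
- Testing during treatment: "Serum pregnancy testing will be performed on Day 1 of each cycle and at EOT for females of childbearing potential".
- Birth control, in broad terms: "Male and female patients should start using birth control from screening throughout the study period up to 6 months after the last dose".
- Enrolment: "If there is any question that a patient will not reliably comply with the contraception requirements, they should not be enrolled in the study".
- The next paragraph obliges patients to agree to a highly effective method, but only those of childbearing potential who are sexually active.

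Schedule footnote 4 repeats the Day 1 test for women of childbearing potential in either arm. Sections 6.1, 11.5 and the Schedule all use that term, and none defines it.

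**The concern.** The waiver names the suppressed group, so this is a stated rule and not an omission. These women may still be able to conceive, and a woman on suppression could be carrying a pregnancy that began before suppression did. Section 6.2 excludes pregnant women, but if 6.1 is followed, nothing clearly requires the test that would show a pregnancy in this group.

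Section 7.1 has staff confirm eligibility by checklist against the inclusion and exclusion criteria, so 6.1 is where they would look. Two staff members could treat the same woman differently, each with support in the text. At stake are possible fetal exposure to a MEK inhibitor plus fulvestrant, and uneven protection between arms that receive the same investigational drug.

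**Working it through.** The plan states no figure here to reproduce. The check compares the provisions for one case: an Arm 1 woman who is not postmenopausal and is receiving a GnRH agonist.

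| Provision | Applies to her? |
|---|---|
| 6.1, Arm 1 contraception and testing | Waived; the parenthesis names her group |
| 6.1, Arm 2 rules for women of childbearing potential | No; Arm 2 only |
| 11.5, serum tests | Only if she is of childbearing potential |
| 11.5, agreement to highly effective contraception | Only if of childbearing potential and sexually active |
| 11.5, broad birth-control sentence | Yes on its wording; it sits poorly with the 6.1 waiver |
| Schedule footnote 4, Day 1 test | Only if she is of childbearing potential |
| 6.2, exclusion of pregnancy | Yes, but orders no test |
| 11.5 and 12.0, withdrawal or removal on pregnancy | Yes, once a pregnancy is known |
| 10.4, concomitant therapy | Permits hormonal therapy and records dates; does not require it to continue |

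**Step 1.** The testing rules and the mandatory contraception rule turn on one question: does a suppressed woman count as being of childbearing potential? No text answers it. The 6.1 parenthesis hints that she does not.

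**Step 2.** If she does not, she has no required test and no required agreement to contraception. The broad sentence in 11.5 remains, and a site must weigh it against an explicit waiver.

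**Step 3.** If she does, 11.5 and footnote 4 apply and contradict 6.1.

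**Step 4.** On either reading, suppression is the only ground for treating her like a postmenopausal woman. No provision requires it to last through treatment or through the 6 months after the last dose, a period in which 11.5 still asks for contraception.

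**Difference in testing.** Under 11.5, for n cycles:

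tests = 1 (screening) + n (Day 1 of each cycle, the first also meeting the 72-hour rule) + 1 (end of treatment) = n + 2

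- n = 2: 1 + 2 + 1 = 4
- n = 6: 1 + 6 + 1 = 8
- Under 6.1: 0

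The cycle counts are illustrative. These figures show how far the two texts diverge. They say nothing about the chance of pregnancy.

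**The case against.** The strongest reply is that the sections can be reconciled. Table 1 and Section 4.1 describe Arm 1 as postmenopausal while 6.1 admits suppressed women, which suggests that suppression was meant as equivalent to menopause. If so, these women are not of childbearing potential, and 6.1 and 11.5 agree on testing and on the mandatory contraception rule. The broad birth-control sentence cannot be taken at full width, since it would then bind postmenopausal women too.

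Much of this stands. A reader might infer that 6.1 and 11.5 flatly contradict each other on contraception. The documents do not support that, because the paragraph after the broad sentence narrows the duty to sexually active patients of childbearing potential. What remains is an undefined term on which both strands depend. If equivalence is intended, the protocol should say so and set the condition that makes it hold, namely continued suppression.

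Other safeguards also count. All patients must be able and willing to follow the whole protocol. Pregnancy is an exclusion, and "any patient who becomes pregnant should be withdrawn from the study". Appendix I lists pregnancy testing, as required, within the standard blood draws at screening, every Day 1 and end of treatment. So testing is available, and it would be wrong to infer that the plan lets known pregnancies through. But these provisions either act on a pregnancy already known or leave open whether a test is required for this group.

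Arm 1 patients must also have progressed on at least one line of therapy for metastatic disease, which should have included endocrine therapy with a CDK4/6 inhibitor. That makes a pregnancy predating suppression a remote scenario. It lowers the likely frequency without closing the gap.

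**Conclusion.** The point holds as a participant-safety gap in a stated rule. As 6.1 is written, a suppressed, non-postmenopausal Arm 1 woman can start treatment without a pregnancy test or a contraception commitment, and nothing requires suppression to continue.

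Its size is 0 tests against n + 2 per affected woman. The number of affected women is not in the documents; that it is small is an assumption. No pregnancy risk can be calculated from the text. Sample size, power and error rates are untouched.

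The conclusion assumes that ovarian suppression alone does not settle childbearing potential. That is a clinical judgement, and the protocol does not state the contrary. This is an inexpensive improvement that should be made.

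**What to change.** **In 6.1:**
- Limit the Arm 1 waiver to postmenopausal or permanently sterile patients.
- State that women who qualify only through ovarian suppression count as women of childbearing potential and follow 11.5 and Schedule footnote 4. That means a serum test at screening, within 72 hours before the first dose, on Day 1 of each cycle and at end of treatment, with highly effective contraception until 6 months after the last dose.
- Require suppression to continue during study treatment.

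**In 11.5:** say that estrogen-containing methods are not suitable for Arm 1. The list of methods opens with "Combined (estrogen- and progestogen-containing) hormonal contraception associated with inhibition of ovulation", while Section 3.3 describes fulvestrant as blocking the action of estrogen. At present 6.1 refers only Arm 2 to that list, so the sentence becomes necessary once Arm 1 women are referred there too.

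**Cost:** a short amendment; n + 2 serum tests per affected woman at visits where blood is already drawn; and possibly a few refusals. Nothing in the statistical plan changes.
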